5.2 Exclusion Criteria

Patients are excluded from the study if any of the following criteria apply:

Medical Conditions

- 1. Patient has tumor involvement of the central nervous system.
- 2. Impaired cardiac functioning or clinically significant cardiac disease, including the following:
 - Acute myocardial infarction or unstable angina pectoris ≤ 6 months prior to starting study drug.
 - Corrected QT interval (QTc) using Fridericia's formula (QTcF) > 470 msec on screening ECG (average of triplicate measurement will be used).
 - Uncontrolled clinically significant cardiac arrhythmia (patients with rate-controlled atrial fibrillation are not excluded).

NOTE: Patients with a history of coronary artery disease, revascularization and/or stable coronary artery disease are not excluded.

 Uncontrolled hypertension despite two concomitant antihypertensive therapies, defined as supine systolic blood pressure ≥ 150 mmHg or diastolic blood pressure > 100 mmHg based on a mean of three measurements at approximately 2-minute intervals.

- 4. Patients who have had a colectomy (total or left hemicolectomy) with re-anastomosis.
- 5. Patients for whom administration of the suppositories are likely to cause pain or difficulties in absorption (e.g., inflamed hemorrhoids, fissures or lesions of the anus or rectum).
- 6. Patients with fecal impaction or uncontrolled irritable bowel disease.
- 7. Patients with inflammatory bowel disease (e.g., Crohn's disease or ulcerative colitis) will be excluded, even if the condition is well controlled.
- 8. Active or chronic infection with human immunodeficiency virus (HIV), hepatitis B or hepatitis C. Screening of patients with serology testing for these viruses is not required. However, patients who have a past history of viral hepatitis or in whom there is a current suspicion of viral hepatitis will have serology testing for hepatitis B and hepatitis C performed to determine whether there is any current evidence of ongoing infection with these viruses. Patients considered to be at risk for HIV infection should have HIV testing performed. If the test result is negative, the patient will be allowed to participate in the study.

NOTE: Patients with chronic HIV infection, on ongoing treatment with anti-viral medications, who have an undetectable viral load are not considered to be infectious and can be included in this study.

- 9. Any other disease, metabolic dysfunction, physical examination finding or clinical laboratory finding that, in the Investigator's opinion, gives reasonable suspicion of a disease or condition that contraindicates the use of an investigational drug, may affect the interpretation of the results, render the patient at high risk from treatment complications or interferes with obtaining informed consent.
- 10. Patients with oligometastatic disease (fewer than 5 metastatic lesions) amenable to standard therapy will be excluded.
- 11. Major surgery within 4 weeks or minor surgery or biopsy within 1 week of the first dose administration.
- 12. Patients who have had RT to the region of the rectum or will require RT to the region of the rectum during the trial.

NOTE: Metastatic castration-resistant prostate cancer [mCRPC] patients who have received prior prostate or prostate fossa radiation and radiation to nearby lymph nodes, where the rectum is not the target, can be included in this study.

Prior/Concomitant Therapy

- 13. Uncontrolled active infection requiring intravenous antibiotic, antiviral or anti-fungal medications within 14 days before the first dose administration. Infections (e.g., urinary tract infection) controlled on concurrent anti-microbial agents and anti-microbial prophylaxis per institutional guidelines are acceptable.
- 14. Receiving or having received anticancer treatment within the following period prior to the first dose administration:
 - Cytotoxic treatment: 3 weeks.
 - Non-cytotoxic drugs, including small molecule investigational products: 3 weeks or 5 terminal half-lives from plasma (whichever is the longest).
 - Biological products including investigational immune-oncology agents: 4 weeks.
 - Radiation with a limited field for palliation: 4 weeks.
 - Radiation to > 30% of the bone marrow: 4 weeks.
 - Lung radiation: 60 days.
- 15. Patient has received corticosteroids at a dose of > 10 mg prednisone/day or equivalent for any reason within 4 weeks prior to receiving the first dose administration.
- 16. History of hypersensitivity to active or inactive excipients of study drug or drugs with a similar chemical structure or class to the study drug.

Other Exclusions

- 17. Patient is not willing to use suppositories.
- 18. Judgement by the Investigator that the patient should not participate in the study if the patient is unlikely to comply with study procedures, restrictions and requirements.
- 19. Patient has a positive reverse transcription polymerase chain reaction (RT-PCR) test for SARS-CoV-2 prior to Screening or enrollment, or has clinical signs and symptoms consistent with SARS-CoV-2 infection; e.g., fever, dry cough, dyspnea, sore throat, fatigue or positive SARS-CoV-2 test result within 2 weeks prior to Screening. Patients who had symptomatic COVID-19 disease less than 1 month prior to Screening will be excluded. If a patient has had a severe course of COVID-19 (extracorporeal membrane oxygenation, mechanically ventilated) within 4 weeks of Screening, or have any sequelae of infection or ongoing infection, the patient will also be excluded. If the patient has had recent (within previous 14 days) exposure to someone who has COVID-19 symptoms, been in contact with someone

who has tested positive for COVID-19 or visited a COVID-19 treatment facility, the patient may be re-evaluated for participation in the study after undergoing an isolation period of at least 10 days and having a negative SARS-CoV-2 RT-PCR test prior to enrollment.

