8.2.2.4.1 Permitted Medications

Analgesic agents, ADT, bisphosphonates and denosumab are allowed to be used during the study. The Investigator or qualified designee will review the use of analgesic agents taken by the patient as part of the concomitant medications review (see SoA [Table 1-1 (Parts 1 and 2)]).

Anti-microbial agents to control infections (e.g., urinary tract infection) are allowed as per SOC guidelines.

Topical hydrocortisone-containing hemorrhoid cream/ointment and/or cutaneous cream is allowed for the treatment of a perineal and/or anal rash and can be administered straight after study drug administration, and as frequently as required as per institution.

The use of a small amount of water-soluble lubricant is advised before rectal administration. No oil- or wax-based lubricants should be used during rectal administration.

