8.2.2.4.2 Prohibited Medication

The following medications and therapies are not allowed during the study:

- Any concomitant chemotherapy.
- Oral or parenteral glucocorticoids and herbs known to alter PSA levels.
- Other investigational agents.
- Inducers (phenobarbital) and inhibitors (valproic acid, probenecid, atazanavir, gemfibrozil, indinavir) of phase 2 drug metabolizing enzymes are prohibited within 14 days prior to first dose of NOX66 and the rest of the study.

- Based on *in vitro* data, idronoxil may inhibit the activity of cytochrome P450 (CYP) 2C8, CYP2C9, CYP2C19 and CYP3A4 enzymes in human microsomes in a range of 0.457 to 3000 μM and concomitant medication that is metabolized by these enzymes should be used with caution.
- The use of inhibitors of uridine 5'-diphospho-glucuronosyltransferase (UGT) enzymes should be avoided.
- Soya contains a high proportion of isoflavones which may interfere with the bioanalytical assay used for detection of idronoxil (active substance), itself an isoflavone derivative, in plasma and urine samples, thus within 2 days prior to NOX66 administration and for the entire duration of the first cycle of the study, patients must be on a soya free diet. The following types of foods are prohibited: edamame, meat alternatives, miso, soymilk, soy nuts, soy sauce (tamari, shoyu and teriyaki), tempeh, and textured soy protein. Trace or very small amounts of soy in foods are permitted.

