9.2 Sample Size Determination

The primary objective of this study is to characterize the safety and tolerability of NOX66 and thereby inform the RP2D of NOX66 for future clinical studies in patients with mCRPC and other solid tumors. Hence, for Part 1 and Part 2 the number of patients has been chosen with the aim to obtain adequate safety, tolerability, safety, PK, and PD profile data while exposing as few patients as possible to the study treatments and procedures.

The sample sizes selected for this study are as follows:

- Part 1 (Dose Escalation): Up to 30 patients will be enrolled in Part 1, in cohorts of 3 to 6 patients (Dose Cohort 1) or 3 to 8 patients (Dose Cohorts 2 to 4) at each specified dose.
- Part 2 (Dose Expansion): A total of 40 patients with mCRPC will be enrolled in Arm 1 and 24 to 30 patients (12 to 15 patients per tumor type [BC and NSCLC]) will be enrolled in Arm 2. The sample sizes for Part 2 were selected to provide sufficient observations for the estimation of endpoints and to assess any signal of efficacy following NOX66 and EBRT treatment.

9.3 **Populations for Analyses**

For purposes of analysis, the following analysis sets are defined:

Population (Analysis Set)	Description
Full Analysis Set (FAS)	The FAS comprises all patients who received at least one dose of study drug.
Safety Analysis Set	The Safety Analysis Set consists of all patients who received at least one dose of study drug. In this study, the Safety Analysis Set will be the same as the FAS.
	This analysis set will be the primary analysis set for all safety endpoints.
Per Protocol Set (PPS)	The PPS consists of all patients in the FAS with $\ge 80\%$ treatment compliance and without major protocol deviations.
PK Analysis Set	The PK analysis set consists of all patients in the Safety Analysis Set and who have at least one idronoxil or metabolite plasma concentration value.
Biomarker Analysis Set	The Biomarker Analysis Set consists of all patients in the Safety Analysis Set and who have at least one plasma biomarker concentration value.

Table 9-1Populations for Analysis

Separate summaries may be provided for patients participating in Parts 1 and 2.

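### Low-dose systemic steroids are tolerated at entry but listed as prohibited on study, and nothing fixes when they must stop relative to the baseline PSA

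*Combined protocol and SAP*

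**What the plan says.** **Entry rule.** Exclusion 15 (Section 5.2, repeated in the Synopsis) removes a patient who has had "corticosteroids at a dose of > 10 mg prednisone/day or equivalent for any reason within 4 weeks prior" to the first dose. A dose of 10 mg/day or less is not excluded.

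**On-study rule.** Section 8.2.2.4.2 opens with "The following medications and therapies are not allowed during the study" and includes the item "Oral or parenteral glucocorticoids and herbs known to alter PSA levels". The item carries no dose threshold, no tumour-type restriction and no period before the first dose. Another item in the same list does carry one: inducers and inhibitors "of phase 2 drug metabolizing enzymes are prohibited within 14 days prior to first dose of NOX66 and the rest of the study".

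**Permitted list.** Section 8.2.2.4.1 says "Analgesic agents, ADT, bisphosphonates and denosumab are allowed to be used during the study". The only steroid it names is topical: "Topical hydrocortisone-containing hemorrhoid cream/ointment and/or cutaneous cream is allowed for the treatment of a perineal and/or anal rash".

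**PSA measurement.** Section 8.1.1 collects PSA at Screening, on Day 1 of Cycles 1 to 5, and on Day 1 of every second cycle after that. Section 9.4.1 takes as baseline the last value before the first NOX66 dose. The Arm 1 primary endpoint (Section 9.4.6.2) is the proportion with a PSA fall of at least 30% from baseline at the end of Cycles 3 and 6, in 40 patients with no control arm.

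**The concern.** A patient who meets the entry rule while taking a low-dose systemic steroid falls under the on-study prohibition, and no text links the two rules. The patient's steroid status when the baseline PSA is drawn is left to the site.

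If the baseline is drawn on steroid and the response samples off it, the change from baseline mixes a change in steroid use with the effect of NOX66 plus radiotherapy. Arm 1 has no concurrent control in which the same change would show, so any effect on PSA passes directly into the reported response rate. If the steroid is continued instead, the patient is on a listed prohibited medication from the first dose, and sites may record that differently.

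**Working it through.** The plan gives no figure to reproduce here: Section 9.1 specifies no hypothesis test, and Section 9.2 gives no calculation behind the 40. The check is mainly a comparison of passages.

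**1. Does any other provision settle it?**

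| Provision | Effect on a patient taking 10 mg/day or less |
|---|---|
| Exclusion 15 | Not excluded |
| Section 6.3, central enrolment check | Checks inclusion and exclusion criteria, so Exclusion 15 raises no flag |
| Section 8.2.2.4.1 | Names topical hydrocortisone only; no systemic steroid |
| Section 6.5, case-by-case clause | Covers other concomitant medication and refers to the prohibited list; does not say that it overrides the list |
| Section 8, opening text | Rules out waivers |
| Section 8.2.2.4.2 | Prohibits, with no stated threshold or stopping date |

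None of these states what the patient should do, or when.

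**2. What does the PSA qualifier modify?**

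- If it modifies herbs only, the glucocorticoid item stands without qualification for every tumour type.
- If it modifies both, either all glucocorticoids are being described as altering PSA, or only those that do so are barred. Sites would have to decide which, and whether the item matters outside mCRPC.

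**3. When could the steroid stop relative to the baseline PSA?**

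- Screening lasts up to 27 days (Days -28 to -2). Cycle 1 is 21 days and later cycles are 14 days.
- End of Cycle 3: 21 + 2 × 14 = 49 days after the start of treatment.
- End of Cycle 6: 21 + 5 × 14 = 91 days.
- Both response times lie well inside the period covered by the prohibition.

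| Patient's course | Baseline PSA | Response PSA | Prohibited use after first dose |
|---|---|---|---|
| Stopped before or during Screening, baseline drawn afterwards | Off steroid | Off steroid | No |
| Stops at first dose, after the baseline draw | On steroid | Off steroid | No |
| Continues | On steroid | On steroid | Yes |

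The text allows the first course but does not require it. Only the second mixes a steroid change into the endpoint. The third keeps the condition constant but is a deviation on the plain reading. Because no washout is set, carry-over is also possible in the first course.

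**4. Size per patient.** With n = 40, one changed response status moves the proportion by 1/40 = 2.5 percentage points; k patients move it by k × 2.5.

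| k (illustrative) | Shift in points |
|---|---|
| 1 | 2.5 |
| 2 | 5 |
| 4 | 10 |
| 8 | 20 |

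For scale, the exact Clopper-Pearson 95% interval is 16.6% to 46.5% for 12/40 (30%) and 20.6% to 51.7% for 14/40 (35%). A two-patient shift is small beside that width. But it is a shift in what is being estimated, and the interval does not allow for it.

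**The case against.** **The two rules cover different periods and can both be met.** Exclusion 15 looks back over the 4 weeks before first dose; Section 8.2.2.4.2 looks forward. A tolerant look-back followed by an on-study prohibition is a coherent design. This stands: the difference in thresholds is not in itself an error, and what is missing is the link between the rules. A reader might infer that every eligible steroid user must either deviate from Day 1 or stop between the baseline and on-study PSA. The documents do not support that, because a patient may stop during Screening or may already have stopped.

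**The prohibition may already apply before first dose.** The enzyme item treats the days before dosing as if they belonged to the study, which suggests that the steroid prohibition could start in Screening. The opposite inference is equally available: one item needed an explicit pre-dose window and the steroid item has none. If it does start in Screening, it covers much of the same period in which Exclusion 15 tolerates 10 mg/day or less, so the passages still need reconciling.

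**Other safeguards exist.** Inclusion 1 ties consent to the protocol's restrictions. Exclusions 9 and 18 let the Investigator decline patients whose condition could affect interpretation or who are unlikely to comply. Section 6.5 sends questions to the Medical Monitor. These reduce the risk but set no stopping time, and leave sites free to differ.

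**The scope of the prohibition is uncertain.** A reader might take it to apply at any dose. Those words are not in the text; the reading comes from the absence of a threshold, and the PSA qualifier could narrow it. This stands, and is itself a reason to clarify.

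**The Per Protocol consequence is slight.** A reader might infer that steroid deviations would remove patients from the main efficacy result. Section 9.3 defines a Per Protocol Set without major deviations but does not class steroid use as one. Section 9.4.7.2, which covers PSA response, bases its efficacy analyses on the FAS, and no analysis in Section 9.4 is assigned to the Per Protocol Set.

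**Conclusion.** The concern holds as a gap between an entry rule and an on-study rule, with a specific consequence for the Arm 1 primary endpoint: a site could follow the text and still draw the baseline PSA on steroid and both response PSAs off it. For breast cancer and NSCLC, whose primary endpoint is disease control rate, only the question of prohibited use arises.

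The total size cannot be given. The documents state neither how many patients enter on a low-dose systemic steroid nor how many of those would stop before baseline, and they give no direction or magnitude for any PSA effect. The supportable figure is 2.5 points per Arm 1 patient whose response status changes. A reader might infer that a substantial share of the 40 is affected; nothing in the plan supports a particular share.

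The conclusion assumes that at least some Arm 1 patients enter on such a dose, and that a change in systemic steroid use can move PSA. The protocol implies the latter only if its qualifier extends to glucocorticoids. The planned analyses are descriptive, so no test is invalidated; what is at risk is the interpretation of a single-arm response rate.

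**What to change.** Reconcile Exclusion 15, in both the Synopsis and Section 5.2, with Section 8.2.2.4.2. The choice of steroid rule is the sponsor's. The revised text should state:

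1. whether a dose threshold applies on study;
2. which tumour types the rule covers;
3. whether the PSA qualifier modifies glucocorticoids, herbs or both;
4. that the baseline PSA for the Arm 1 primary endpoint is drawn under the steroid condition that will apply on study.

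The fourth statement protects the endpoint whichever rule is chosen, because the change from baseline then no longer spans a change in steroid use required by the protocol.

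The cost is wording at the next amendment, with no new procedures. Depending on the rule chosen, a few patients may start slightly later or become ineligible.

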5.3 Screen Failures

Screen failures are defined as patients who consent to participate in the clinical study but are not subsequently enrolled in the study. A minimal set of screen failure information is required to ensure transparent reporting of screen failure patients to meet the Consolidated Standards of Reporting Trials publishing requirements and to respond to queries from regulatory authorities. Minimal information includes demography, reason for screen failure (e.g., eligibility requirements failed), and any SAEs will be recorded in the electronic case report form (eCRF).

Individuals who do not meet the criteria for participation in this study (screen failure) may be rescreened. This will be assessed on a case-by-case basis and requires Sponsor and Clinical Research organization (CRO)'s prior approval before the patient is rescreened. Rescreened patients should be assigned a different unique participant number from the initial screening. The previous screening number will be noted separately for reference purposes.

5.3.1 Screening and Enrollment Log and Participant Identification Numbers

The patient's enrollment will be recorded in the Screening and Enrollment Log.

Upon screening, each patient will receive a unique participant identification number. Participant numbers must not be re-used for different patients.

6 Study Drug

Study drug is defined as any investigational drug(s) (including marketed product[s]) intended to be administered to a study participant according to the study protocol.

On days when study drug and EBRT are to be administered, it is advised that NOX66 is given at least 1 hour prior to EBRT.

6.1 Study Drug(s) Administered

Details on study drug administered during this study are given in Table 6-1.

]	Pa	rt 2		
Dose Cohort/ Arm:	Dose Cohort 1	Dose Cohort 2	Dose Cohort 3	Dose Cohort 4	Arm 1	Arm 2

Table 6-1Study Drug(s) Administered

Drug Name:	NOX66	NOX66	NOX66	NOX66	RP2D	RP2D	
	800 mg	1200 mg	1600 mg	2400 mg	10.20	10.20	
Туре:			Small n	nolecule			
Dosage Formulation:		Supposite	ory containing id	ronoxil in a lipophi	lic base		
Unit Dose Strength(s):			400 mg c	or 600 mg			
Dosage Level(s):	1 x 400 mg suppository administered twice daily. Total daily dose of 800 mg.	1 x 600 m suppositor administere twice daily Total daily dose of 1200 mg.	y suppositor administer twice daily Total dail dose of	y suppository administered w. twice daily. y Total daily dose of	To be determined	To be determined	
Route of Administration:			Re	ctal			
Use:			Interve	entional			
IMP and NIMP:			IN	1P			
Sourcing:	Provided central	ly by the Spo	nsor.				
Dosing Instructions:	Twice daily NOX66 dosing should occur at least 10 hours apart. Where 2 suppositories are administered per dosing, each suppository will be administered at least 5 minutes apart. The same administration schedule should be adhered to on the days when EBRT is administered. Patients or care givers should always wear gloves when handling and/or during administration of NOX66. The use of a small amount of water-soluble lubricant is advised before rectal administration. No oil- or wax-based lubricants should be used during rectal administration. Patients will be provided with an "Instructions for Administration of NOX66 Suppositories" that contains further details.						
Packaging and Labeling:		riate quantitie		ealed PVC supposit study. Each box v			

IMP = investigational medicinal product; RP2D = recommended Phase 2 dose

From Cycle 3 onwards, study drug for 2 cycles will be dispensed every second cycle (i.e., Cycles 5, 7, 9, 11 etc.). From Cycle 5 onwards, on-site visits will occur on a 28-day (4 weekly) basis, i.e., patients will visit the clinical unit every second cycle. After Cycle 5, the next patient visit will therefore be Cycle 7, followed by Cycle 9, etc. until the patient completes the treatment period or is withdrawn.

In patients who have regular bowel movements (i.e., within several hours after waking), patients will be instructed to insert the suppository after the bowel movement. To promote regular bowel movements, patients should be encouraged to consume a high fiber diet, with adequate amounts of water. In those patients who are not on a regular bowel movement schedule, insertion of the

suppository should occur at regularly scheduled times individualized for the patient (but approximately 10 hours apart).

For Days 1, 2, 6 and 14 of Cycle 1 and Day 1 of Cycles 2 and 3 (PK days), once the suppository is inserted in the rectum and defecation occurs within 2 hours after the administration, the remaining doses should be administered at the prescribed time as scheduled. No re-dosing is permitted if defecation occurs within 2 hours of administration.

The dosing time for suppository/ies administration must be recorded by the patient in the Patient Study Drug Administration Diary which must be brought to the study center at each on-site visit.

